### 4 STUDY DESIGN AND ENDPOINTS

#### 4.1 DESCRIPTION OF THE STUDY DESIGN

This study is a randomized crossover trial consisting of two test visits separated by a washout period of 3 to 5 weeks. Subjects are randomized into two equal groups. Group 1 receives DCTclock-pen at the first visit, with the DCTclock-tablet given at the second visit; Group 2 receives DCTclock-tablet at the first visit, followed by DCTclock-pen at the second visit. At Visit 1 (day 0), eligibility is assessed and a version of the DCTclock test is administered based on the group allocation. A battery of Linus Platform tests and reference standard tests are also administered. At visit 2 (day 21-35), eligibility is assessed and the alternate version of the DCTclock test is administered based on the group allocation. A battery of Linus Platform tests is also administered, together with reference standard tests. Equivalence of DCTclock-pen and DCTclock-tablet will be tested. Linus Platform test data will be collected to develop novel measures of cognitive and motor function and assess their accuracy in detecting impairment, construct validity, and test-retest reliability. 200 subjects will be recruited to participate with the anticipation that 175 will be available for analysis.

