#### **Linus Platform decision making and reaction time tests (4)**

Participants will be asked to complete three short cognitive tasks presented on a tablet supplied by the study. These tasks are sourced from DANA Brain Vital (Anthrotronix, Inc.), which is an FDA-cleared, modular application that measures cognitive efficiency by tracking subtle changes in cognitive capabilities. DANA assessments are highly sensitive and designed for high-frequency use and focus on accuracy and reaction time—two key elements of cognitive efficiency. Each task takes 1-2 minutes to complete. Subjects will also be asked to complete the PHQ-9 depression screening tool (13). An iPad application captures, encrypts, and transmits the encrypted data to Linus' HIPAA compliant servers.

The tasks included are as follows:

Task	Description
Simple Reaction Time	A bullseye stimulus appears on the screen, and the test taker taps it as quickly as possible
Procedural Reaction Time	A number (1, 2, 3 or 4) appears on the screen, and the test taker must indicate which number was displayed by tapping either the “1 or 2” button or the “3 or 4” button
Go/No-go	A building with six windows is displayed, and either a “friend” (green) or “foe” (gray) alien will appear in a window. The test taker must tap the “BLAST” button only when foe stimuli appear
PHQ-9	Self-reported depression screening tool

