**DCTclock (tablet and pen) and Linus platform drawing tasks-** Data from these tests includes time-stamped coordinate level details of the drawing process. It is encrypted at the time of collection (either on the digital pen or iPad) and transmitted by way of a locally installed data transfer application directly to the sponsor's HIPAA compliant servers, at which point they are deleted from the input device (tablet or pen).

**Linus Platform reaction time and gait assessments-** Data from these tasks includes millisecond-level precise measurements of reaction time to tablet screen stimuli as measured by the tapping of buttons on the tablet (reaction time) and gyroscope and accelerometer readings collected on a smartphone (gait). These measurements are stored locally on the tablet/smartphone with encryption before transmission directly to the sponsor's HIPAA compliant servers, at which point they are deleted from the device.

**Linus Platform Lifestyle questionnaire and PHQ-9-** Data from these tasks include fixed 'yes/no' and 'not at all/several days/more than half the days/nearly every day' answers to questions presented to the participant on the tablet. These responses are stored locally on the tablet with encryption before transmission directly to the sponsor's HIPAA compliant servers, at which point they are deleted from the device.

**Linus Platform speech analysis-** Speech recordings and meta data about the speech session are stored locally on the tablet with encryption until they are successfully uploaded to the sponsor partner's HIPAA compliant web servers, at which point they are deleted from the device. The data is encrypted in transit and at rest on the servers. All data is hosted on AWS behind secure API gateways and is access-controlled so that only trained and approved employees can access it. Meta data only includes non-identifying information, such as time & date for the session and information about the study supplied tablet device. Audio is also sent to a HIPAA compliant transcription provider for transcription. The resulting raw audio samples, transcripts, and analysis of the voice recording transferred to the sponsor will include details such as phonation and respiratory control.

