11 OTHER PLANNED ANALYSES

11.1 AGREEMENT WITH MMSE AND RBANS ANALYSES

Linus Platform individual tests will be compared to MMSE and RBANS to measure agreement in assessment of cognitive status in the Evaluable Population. Additionally, Linus Platform individual tests will be combined to obtain a Linus overall score (Linus score) to measure cognitive status: the training dataset will be used to create a Linus score based on the individual Linus Platform tests and the Evaluable Population will be used to validate the Linus score by assessing its agreement with MMSE and RBANS. I.e., all analyses below will be carried out on the Evaluable Population.

Since most of the Linus Platform tests are administered twice (once at visit 1 and once at visit 2), the RBANS is administered twice (at visit 1 and visit 2) and the MMSE is only administered once (at visit 1) the following sets of comparisons will be made:

1. MMSE at Visit 1 vs. Individual Linus Platform Score or Developed Linus Score at Visit 1
2. RBANS at Visit 1 vs. Individual Linus Platform Score or Developed Linus Score at Visit 1
3. RBANS at Visit 2 vs. Individual Linus Platform Score or Developed Linus Score at Visit 2

For each pairing of the individual Linus Platform scores or the developed Linus score and the reference standard MMSE and RBANS (Reference score), agreement analyses will be carried out as follows:

- Linus scores will be standardized by taking the subject's Linus score, subtracting by the overall Linus score mean and dividing by the overall Linus score standard deviation. This method will also be used to standardize the MMSE scores and RBANS scores. To better visualize the relationship between the two tests, the standardized Linus score will be plotted separately against a standardized reference score (either MMSE or RBANS) in a scatter plot, superimposed with a line of identity.
- Linear and rank linear regression analyses will be conducted and p-values with 95% CI will be calculated for the y-intercept and slope of each model. Either the Pearson (linear regression) or the

Spearman (rank regression) correlation coefficients will be produced and superimposed onto the scatter plots for each regression method, along with 95% CIs and the estimated regression line. In these regressions, the dependent variables are either the individual Linus Platform score or the developed Linus scores and the independent variables are either the MMSE scores or the RBANS scores.

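### SAP 11.1 labels as agreement a set of exploratory analyses that can show only association, does not align score direction, validates the Linus score on subjects used to build it, and never estimates how well any test detects impairment

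*SAP*

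**What the plan says.** SAP 11.1 covers every pairing of a Linus Platform test, or the combined Linus score, with MMSE or RBANS, and states that "agreement analyses will be carried out as follows". There are two steps.

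- **Plot.** Each Linus score is standardized by "subtracting by the overall Linus score mean and dividing by the overall Linus score standard deviation", and MMSE and RBANS are treated in the same way. The standardized Linus score is then "plotted separately against a standardized reference score (either MMSE or RBANS) in a scatter plot, superimposed with a line of identity".
- **Regression.** For linear and rank regressions, "p-values with 95% CI will be calculated for the y-intercept and slope of each model". Here "the dependent variables are either the individual Linus Platform score or the developed Linus scores", and MMSE or RBANS is the independent variable. Pearson or Spearman coefficients with 95% CIs and the fitted line are drawn on the scatter plots. This step does not say whether the regressed scores are standardized.

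The tests listed in SAP 3.2.3 include the reaction time tests, the lifestyle questionnaire and PHQ-9, which Protocol 6.1 describes as a "Self-reported depression screening tool". Protocol 4.1 says the Linus data will be used to "assess their accuracy in detecting impairment, construct validity, and test-retest reliability"; the Protocol Summary and SAP Section 2 say the same. SAP 11.1 builds the Linus score on the training set and validates it on the Evaluable Population.

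**The concern.** Agreement asks whether two measures give the same value, so it concerns location and scale. Z-scores have had both removed. A plot of z-scores against an identity line therefore cannot show agreement, and it invites the reader to treat any departure from the line as disagreement. If a score runs the other way (longer time means worse performance), a valid test slopes against the line.

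These outputs are the evidence for Aim 3, which is to develop and validate the Linus tests. As planned, they would print intercept tests with no useful meaning and carry an agreement label they cannot support. They would give no pre-specified estimate of how well a test separates impaired from unimpaired subjects. The Linus score would also be assessed largely on its own training data.

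**Working it through.** The documents give no numerical target for SAP 11.1, so there is no figure to reproduce. The stated sample size of 41 belongs to the primary Bland-Altman test.

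**1. Regression on z-scores (same subjects and visit).** For a regression of y on x, slope = r × SD(y)/SD(x) and intercept = mean(y) − slope × mean(x). With both means 0 and both SDs 1, slope = r and intercept = 0. Simulated pairs at N = 175 gave intercept 0 (p = 1.00) and slope equal to r in every run: 0.3135, 0.6547, 0.9011 and −0.5267. Multiplying the Linus score by 3 and adding 50 changed neither, so bias or a scale difference cannot appear. The fitted line y = r·x crosses the identity line at the mean. For r < 1 it lies below identity above the mean and above identity below the mean. It coincides with identity only at r = 1.

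**2. Regression on raw scores.** The intercept is the predicted Linus score at an MMSE or RBANS of 0, and the slope is in Linus units per reference point. The slope p-value was the same on raw and z-scores in every run, so on either scale it tests only for zero association.

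**3. Other readings.**
- Rank regression without ties has slope equal to Spearman rho and intercept (N+1)/2 × (1 − rho). At N = 175 and rho = 0.6001 this is 88 × 0.3999 = 35.19, which carries no further information.
- If the overall mean and SD are pooled over visits, the intercept need not be 0. With assumed practice gains of 0.2 SD (reference) and 0.4 SD (Linus), simulated intercepts were −0.15 at Visit 1 and +0.16 at Visit 2. They reflect the visit shift, not agreement.

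**4. Direction.** Protocol 13.4 says the reaction-time data are "millisecond-level precise measurements of reaction time to tablet screen stimuli", and Protocol 6.1 asks for fast responses. If the analysed score stays a time, a valid test has r < 0 and a negative slope on the plot. The analysed direction of the other tests, PHQ-9 included, is not given.

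**5. Accuracy.** Neither document plans sensitivity, specificity, an ROC curve or AUC, or sets an MMSE or RBANS impairment cut-off for analysis. SAP 11.3 models whether a person falls in the same category on both assessments. That is consistency, not accuracy against a reference.

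**6. Overlap.** SAP 6.3 and 6.4 split the Evaluable Population into 50 validation subjects and the rest for training. With 175 evaluable, 175 − 50 = 125, and 125/175 = 71% of the validating set would have been used to build the Linus score.

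**7. Precision of an AUC (Hanley-McNeil).** SE² = [A(1−A) + (n₁−1)(Q₁−A²) + (n₂−1)(Q₂−A²)]/(n₁n₂), with Q₁ = A/(2−A), Q₂ = 2A²/(1+A), n₁ impaired and n₂ unimpaired. At an assumed A = 0.85, Q₁−A² = 0.0166 and Q₂−A² = 0.0586. Prevalence is not given in the documents, so a range is shown.

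| N | Assumed prevalence | n₁ / n₂ | SE |
|---|---|---|---|
| 175 | 20% | 35 / 140 | 0.042 |
| 175 | 30% | 52 / 123 | 0.036 |
| 175 | 40% | 70 / 105 | 0.032 |
| 50 | 30% | 15 / 35 | 0.067 |

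**The case against.** Much can be said for the plan, and several stronger readings do not survive.

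- **Intercept always 0 and slope always r.** A reader might infer this from the z-score plots. The SAP introduces standardization only to help visualize the relationship and does not repeat it for the regressions, though their line is drawn on those plots. The result holds only for z-scores from the same subjects and visit. The safe statement is that the scale is not stated and that no reading yields agreement.
- **Time-scored tests would show twice the disagreement.** The SD of the z-difference, √(2(1−r)), is 0.89 at r = 0.6 and 1.79 at r = −0.6. SAP 11.1 never computes that quantity. It does print the correlation with its CI, and −0.6 shows both strength and direction. The risk lies in how the plot is read.
- **Score direction is known.** Protocol 13.4 describes captured data, not the analysed score, and Protocol 6.1 describes the reaction-time source as measuring cognitive efficiency. The point is therefore conditional on a score being kept as a time.
- **An endpoint is left unanalysed.** Detecting impairment accurately is a purpose in the design text, not a listed endpoint. The listed exploratory endpoints have analyses, and SAP Section 2 allows further exploratory work. What is missing is pre-specification.
- **The lifestyle questionnaire does not belong.** Protocol 6.1 says its questions relate to cognitive performance, so comparing it with RBANS is reasonable. Only the agreement label is not.

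What stands is the label, the identity line, the intercept tests, the unaligned direction, the absent accuracy analysis and the training overlap.

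**Conclusion.** The concern holds in this bounded form. On every reading, the outputs of SAP 11.1 measure association and cannot establish agreement. The planned Pearson and Spearman coefficients with CIs are useful and should stay. The identity line and intercept p-values add nothing and may mislead where a score is kept as a time. One purpose stated in both documents has no planned estimate. About 71% of the subjects validating the Linus score would also have built it, assuming 175 evaluable and the 50-subject split. The analyses are exploratory, so the primary and safety conclusions are unaffected. The change is worth making because it alters what Aim 3 can conclude.

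**What to change.** In SAP 11.1 and the matching Appendix A shells:

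1. State the analysed direction of each score and orient all scores so that higher is better before standardizing. State the regression scale, and which subjects and visits supply the mean and SD.
2. Call the analysis association (construct validity). Drop the identity line and the intercept p-values. Keep the Pearson and Spearman coefficients with 95% CIs.
3. Report PHQ-9 and the lifestyle questionnaire as correlates, not as agreement in cognitive status.
4. Report the AUC with 95% CI of each Linus test against one impairment definition fixed before analysis from data already collected, for example the current dementia or MCI recorded for SAP 8.4. Otherwise remove the accuracy purpose from the design text.
5. Assess the combined Linus score only in the Validation Population, as Protocol 10.3.4.1 has it.

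The cost is SAP and shell wording; no new data are needed. There are two drawbacks. Recorded diagnosis is an imperfect reference. Precision is also limited: in 50 subjects at 30% prevalence the AUC interval is about ±1.96 × 0.067 = ±0.13, so the Linus score result would be honest but wide.

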11.2 TEST-RETEST RELIABILITY ANALYSES

Subjects will undergo cognitive testing with both the Linus Platform tests and the reference standard RBANS twice, where the second examination will be three to five weeks after the first examination. Test-retest reliability of both individual Linus Platform tests and the combined Linus score will be compared to the test-retest reliability of the RBANS. For the analysis, subjects who no longer satisfy the inclusion/exclusion criteria prior to the second examination will be excluded.

For, the individual Linus Platform scores, the developed Linus score, and the reference standard RBANS, agreement analyses will be carried out as follows:

- Agreement between the first and second measurements will be measured. A scatter plot of measurement 2 vs. measurement 1 will be generated, superimposed with a line of identity. An unweighted Deming regression (where the variance of the measurement error is determined by the two measurements that were collected 3-5 weeks apart) will be carried out to determine the y-intercept, slope and their two-sided 95% CIs. The ICC will also be determined.
- A hypothesis test of the slope vs. 1 and of the y-intercept vs. 0 will be carried out. Specifically, the following hypothesis test will be carried out: $H_0: \beta_0 = 0$ vs. $H_1: \beta_0 \neq 0$ and $H_0: \beta_1 = 1$ vs. $H_1: \beta_1 \neq 1$ where β_0 and β_1 are the y-intercept and slope, respectively, from the Deming unweighted regression. Each of these will be carried out at a two-sided 0.05 level of significance.

The Evaluable Population will be used for these analyses.

In addition to the above, descriptive statistics (N, mean, standard deviation, median, minimum and maximum) of the Visit 1, Visit 2 and the difference between Visit 1 and Visit 2 (calculated as Visit 1

minus Visit 2) will be presented for the RBANS score, for the Linus total score and for the Linus Platform individual test scores.

Figures will display the above described plots and the associated statistics (y-intercept and slope and their Cis, ICC, estimates of β_0 and β_1 from the Deming regression, and the p-values from the test of the Deming null hypotheses).

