##### 10.3.4.2 TEST-RETEST RELIABILITY

Participants will undergo cognitive testing with both the Linus Platform tests and the reference standard RBANS twice, where the second examination will be three to five weeks after the first examination. Test-retest reliability of both individual Linus Platform tests and the combined Linus score will be

compared to the test-retest reliability of the RBANS. For the analysis, participants who no longer satisfy the inclusion/exclusion criteria prior to the second examination will be excluded.

For, the individual Linus Platform scores, the developed Linus score, and the reference standard RBANS, agreement analyses will be carried out as follows:

- Agreement between the first and second measurements will be measured. A scatter plot of measurement 2 vs. measurement 1 will be generated, superimposed with a line of identity. An unweighted Deming regression (where the variance of the measurement error is determined by the two measurements that were collected 3-5 weeks apart) will be carried out to determine the y-intercept, slope and their two-sided 95% confidence intervals. The correlation coefficient will also be determined.
- A hypothesis test of the slope vs. 1 and of the y-intercept vs. 0 will be carried out. Specifically, the following hypothesis test will be carried out:

$$H_0: \beta_0 = 0 \text{ vs. } H_1: \beta_0 \neq 0 \text{ and } H_0: \beta_1 = 1 \text{ vs. } H_1: \beta_1 \neq 1$$

where  $\beta_0$  and  $\beta_1$  are the y-intercept and slope, respectively, from the Deming unweighted regression.

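### The promised comparison of Linus with RBANS test-retest reliability has no specified contrast or interval, and the only hypothesis tests in SAP 11.2 (Deming slope = 1, intercept = 0) address shift between visits, not reliability

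*SAP*

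**What the plan says.** Protocol 10.3.4.2 and SAP 11.2 state the same exploratory aim. In the SAP's words: "Test-retest reliability of both individual Linus Platform tests and the combined Linus score will be compared to the test-retest reliability of the RBANS".

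The SAP then lists analyses to be run on each score by itself:

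- A scatter plot of visit 2 against visit 1 with the identity line.
- A Deming fit: "An unweighted Deming regression (where the variance of the measurement error is determined by the two measurements that were collected 3-5 weeks apart"). Slope and intercept get 95% CIs.
- "The ICC will also be determined". The protocol has "The correlation coefficient will also be determined" at the same place.
- "A hypothesis test of the slope vs. 1 and of the y-intercept vs. 0 will be carried out", and "Each of these will be carried out at a two-sided 0.05 level of significance".
- Descriptive statistics for visit 1, visit 2 and their difference.

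The analysis set is given as follows: "The Evaluable Population will be used for these analyses". The figures are to print the Deming estimates, their p-values and the ICC. The test-retest table in SAP Appendix A holds only means, SDs, medians and ranges.

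**The concern.** The aim is a contrast between two reliabilities, but no such contrast is defined. There is no difference in ICC, no interval for any ICC, no margin, and no rule for reading two scores side by side. The form of the ICC is not named either, although consistency and agreement forms separate once scores move between visits. SAP 9.2 anticipates such learning on DCTclock.

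The only p-values in the section come from tests of slope and intercept. These ask whether scores move systematically between visits. Reliability depends on random within-subject error, which the tests do not address. A non-significant result could therefore be taken as support for reliability when it carries none. At stake is part of Aim 3, the development and validation of the Linus tests.

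**Working it through.** **The plan's own figure.** None exists. Neither document gives a target, power or criterion for test-retest reliability.

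**What the Deming tests examine.** Let s_xx and s_yy be the visit 1 and visit 2 variances, s_xy the covariance, and the error-variance ratio 1 (an assumption; one score per visit does not by itself identify the ratio). Then

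b = [(s_yy − s_xx) + √((s_yy − s_xx)² + 4 s_xy²)] / (2 s_xy), and a = ȳ − b x̄.

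Setting b = 1 with s_xy > 0 gives √(d² + 4 s_xy²) = 2 s_xy − d, where d = s_yy − s_xx. Squaring leaves 4 d s_xy = 0, so d = 0. Slope 1 thus means equal variances at the two visits, and with slope 1 an intercept of 0 means equal means. If both visits have variance σ² and covariance ρσ², then b = 1 for every reliability ρ > 0.

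**Simulation inputs.** N = 175 is the number expected to be available for analysis (Protocol 4.1). Each test is two-sided at 0.05 (SAP 11.2). The following are assumptions, not in the documents: reliability 0.2 to 0.95, size of shift or slope change, score mean/SD of 100/15 or 50/20, and error ratio 1. Visit 1 = T + e₁; visit 2 = shift + slope × T + e₂. Standard errors are jackknife.

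Percentage of trials in which neither null is rejected:

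| Assumed truth | ρ = 0.2 | 0.4 | 0.6 | 0.8 | 0.9 | 0.95 |
|---|---|---|---|---|---|---|
| No shift, slope 1 | 92-95 | 92-95 | 92-95 | 92-95 | 92-95 | 92-95 |
| Shift 0.2 SD, 100/15 | 92 | 92 | 92 | 89 | 82 | 76 |
| Shift 0.2 SD, 50/20 | 89 | 90 | 85 | 70 | 46 | 15 |
| Shift 0.4 SD, 50/20 | 86 | 80 | 62 | 26 | 2 | 0 |
| Slope 1.15, 100/15 | 97 | 93 | 74 | 28 | 3 | 0 |

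With true slope 0.85, slope = 1 is rejected in about 13-16%, 26%, 53% and 97-98% of trials at reliability 0.3, 0.5, 0.7 and 0.9. With no shift it is rejected in about 4-7% throughout.

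**Why the ICC form matters.** Take reliability 0.9, unit variance and a shift of 0.4 SD. The consistency ICC stays at 0.90. The agreement ICC adds the between-visit variance 0.4²/2 = 0.08 to the denominator: 0.90/1.08 = 0.83.

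**Is the missing comparison feasible?** Assume an RBANS ICC of 0.85, true-score correlation 0.6, and the same 175 subjects for both scores. For the paired difference in agreement ICCs:

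| Linus ICC | SE of difference | 95% CI half-width | Power against zero |
|---|---|---|---|
| 0.60 | 0.052 | 0.10 | about 100% |
| 0.70 | 0.041 | 0.08 | 95% |
| 0.75 | 0.037 | 0.07 | 76% |
| 0.80 | 0.032 | 0.06 | 34% |

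For the third row, 1.96 × 0.037 = 0.07.

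**Which tests have a retest.** The schedule in Protocol 7.3.4 places eye tracking, the lifestyle questionnaire, PHQ-9 and every speech task except list learning at visit 2 only. The test-retest table shell omits the first two, but still has rows for PHQ-9 and all the speech tasks.

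**The case against.** The strongest reply is that the section does plan a reliability measure. The ICC is to be computed for the RBANS, the Linus score and each Linus test, in one population over one interval, and printed on each figure. The shell adds the SD of the between-visit difference. A descriptive side-by-side reading is therefore available, and a noisy test would show: the median width of the slope CI is about 1.4 at reliability 0.2 and 0.10 at 0.95. The endpoint is exploratory, and the missing intervals could be computed later from the same data. All of this stands. It limits the gap to an unspecified contrast, missing intervals and an unnamed ICC form.

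Three stronger readings are tempting, and the documents do not support them.

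- A reader might infer that a test passes more easily the less reliable it is. SAP 11.2 sets no pass rule, in contrast to SAP 9.1, which defines success for the primary endpoint. The gradient also needs a real slope change or a sizeable shift. Without one the rate is flat, and at N = 50 with a 0.2 SD shift on the 100/15 scale it is nearly so (90% at reliability 0.2, 87% at 0.95).
- A reader might infer that a poor test could be shown to beat the RBANS. That would require ignoring the ICC printed on the same figure.
- A reader might infer that nothing planned bears on the comparison. The ICCs do, descriptively.

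**Conclusion.** The concern holds in limited form. SAP 11.2 promises a comparison with the RBANS and supplies its ingredients, but neither the contrast nor any measure of its uncertainty. Its only hypothesis tests answer a different question. That the Deming tests are silent on reliability follows from the algebra under an error ratio of 1. The non-rejection rates and the precision of the ICC difference rest on the assumed reliabilities, shifts, ICCs and correlation stated above. The planned N would support a useful interval: half-width 0.06 to 0.10 for a Linus ICC of 0.80 to 0.60. The primary equivalence conclusion and the safety analysis are not affected. This should be put right because it is cheap and lets the endpoint answer its own question.

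**What to change.** In SAP 11.2:

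1. Make the reliability result the two-way, absolute-agreement, single-measure ICC with a 95% CI for the RBANS, the Linus score and each Linus test given at both visits.
2. Add the paired difference in ICC, Linus minus RBANS, with a 95% CI from a bootstrap that resamples subjects and keeps each subject's scores on both instruments at both visits together.
3. Keep the Deming slope and intercept with CIs as a description of shift, and state that their p-values are not evidence of reliability.
4. Limit the analysis to tests repeated at both visits. Remove PHQ-9 and the speech tasks other than list learning from the test-retest table shell, and add the ICC and its difference to that shell.
5. Record in SAP section 12 that the ICC replaces the protocol's correlation coefficient.

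The cost is a short bootstrap program and a revised shell. No new data are needed.
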